## **2 SUMMARY**

**Protocol Title:** HIV Testing and Treatment to Prevent Onward HIV Transmission Among MSM and Transgender Women in Lima, Peru.

**Short Protocol Title:** Test and treat early HIV among MSM and Transgender Women in Lima, Peru

**Study Name:** "¿SABES?"

**Sites:** EPICENTRO; VIA LIBRE; and IMPACTA San Miguel and Barranco Clinical Research Sites at IMPACTA PERU Clinical Trials Unit in Lima, Peru.

**Planned Starting Date:** July 2012

**Planned Ending Date:** July 2016

**Study Rationale:** This research will expand upon Seek-Test-Treat-Retain (STTR) strategies based on HIV testing and treatment of individuals with acute and recent HIV infection. The overall objective is to improve the efficacy of STTR strategies by specifically intervening to reduce the impact of viral load on HIV transmission among individuals with acute and recent HIV infection. This research will be conducted in Lima, Peru. We will investigate the population-level impact of drug and alcohol use on HIV transmission by examining the role of men who have sex with men (MSM) and transgender women who report substance use (mostly alcohol) in transmission clusters identified through partner tracing and phylogenetic analysis. This analysis will investigate the feasibility of incorporating tests for acute HIV infection into routine HIV testing and will model the contribution of men with acute and recent HIV infection to transmission among networked populations, such as MSM and transgender women.

The overall aim of this project is to model STTR strategies that specifically intervene to reduce HIV transmission through reductions in HIV-1 viral load and sexual risk behavior among individuals with early HIV infection, including both acute and recent infections.

### **Primary Objectives**

1. To estimate the impact of immediate and deferred (24 weeks after study enrollment) antiretroviral therapy (ART) on the decay dynamics of HIV viral load in plasma, semen and rectal secretions from individuals with early HIV infection;
2. To investigate the impact of drug and alcohol use on HIV transmission by examining and modeling the role of MSM and transgender women with substance abuse disorders in transmission clusters identified through partner tracing and phylogenetic analysis.

### **Secondary Objectives**

1. To determine HIV incidence and associated risk factors among high-risk HIV-1 uninfected MSM and transgender women who participate in a program of frequent routine HIV testing.
2. To attempt to identify transmission clusters in phylogenetic trees constructed using early viral specimens from study participants with acute or recent HIV infection.

3. To determine other characteristics (sexual risk behavior, partner characteristics, use of entertainment venues, and reason for HIV testing) in MSM and transgender women within clusters compared to those outside of clusters.
4. To assess the feasibility and acceptability of re-contacting HIV-negative individuals with evidence of acute infection (HIV-1 RNA positive) for further HIV testing and linkage to care.
5. To evaluate the frequency of HIV testing among recent sexual partners of participants diagnosed with early HIV-1 infection, comparing strategies such as partner tracing and notification, and general and targeted community outreach.
6. To evaluate retention in care, including adherence to ART and study procedures, among individuals with early HIV-1 infection receiving immediate and deferred ART.

#### **Primary endpoints**

1. To quantify HIV viral load in plasma, semen and rectal secretions in individuals with early HIV infection in immediate versus deferred treatment groups.
2. To identify transmission clusters through phylogenetic analysis among participants with early HIV infection receiving immediate and deferred ART; Construction of models to assess the potential population impact of a seek-test-treat-retain strategy.

#### **Secondary endpoints**

1. To identify risk factors associated with incident HIV-1 infection.
2. To identify sequence clusters using phylogenetic analysis among participants with early HIV infection.
3. To compare sexual risk behavior, partner characteristics, entertainment venue attendance, and method of referral in MSM and transgender women within clusters to those outside of clusters.
4. To determine the proportion of individuals with evidence of acute infection (HIV-1 RNA-positive) who are successfully contacted for confirmatory HIV testing and are then linked to care.
5. To determine the proportion of newly identified HIV-positive men willing to name at least one recent sexual partner, and the proportion of named partners subsequently contacted and tested.
6. To determine the proportion of men retained in care, including adherence to ART and study procedures, among individuals with early HIV-1 infection receiving immediate and deferred ART.

**Design:** This is three-step trial. In Step 1, we will screen MSM and transgender women, unaware of their HIV status and with evidence of high risk for acquiring HIV-1 infection, including risky sexual behavior, a partner of a newly-diagnosed person with acute or recent HIV

## *Test and Treat Early HIV among MSM and Transgender Women in Lima, Peru*

infection or with symptoms of acute retroviral syndrome. We anticipate testing approximately 2400 MSM and transgender women until July 2015. In Step 2, high risk HIV-1 uninfected MSM with high risk sexual behavior will be tested at variable times (during which they will receive standard HIV prevention education) for incident HIV-1. Roughly, we anticipate re-testing approximately 800 MSM and transgender women per month until July 2015. In Step 3, individuals with acute and recent HIV-1 infection detected at Step 1 or 2; or individuals who have been diagnosed with HIV in any health clinic or laboratory authorized by the Ministry of Health, and that have had a documented negative result in the past three months, will be enrolled in a 48-week randomized, open label clinical trial of the effects on the decay dynamics of HIV viral load in plasma, semen and rectal secretions of immediate vs. deferred (by 24 weeks) ART, unless ART initiation criteria are met earlier. We expect approximately 200-250 MSM and transgender women (roughly 100-125 individuals with acute and 100-125 with recent HIV-1 infection).

Those participants, who have started their participation in the study before the approval of **Amendment Letter #1** in this study protocol, will continue their participation as originally programmed.

Once the **Amendment Letter #1** is approved for this study protocol, the participants who are eligible for Step 3 will be given treatment the following way: 1) those people diagnosed with **acute HIV infection** will be offered immediate ART (just at time of the enrollment visit or during the next 48 to 72 hours) for the duration of 48 weeks. 2) The people who are diagnosed with **recent HIV infection** will be randomized to start immediate ART or defer ART initiation until 24 weeks after HIV diagnosis, all of them followed for 48 weeks after which they will continue ART from other sources.

**Intervention:** This is a study of timing of antiretroviral therapy(ART) initiation. This study will not compare one ART medication to another. The ART medications that will be used can be taken as one pill a day so that number of pills taken each day is not a burden for people in the study. Co-formulated elvitegravir/cobicistat/emtricitabine/tenofovir disoproxil fumarate (STRIBILD®) or emtricitabine/tenofovir disoproxil fumarate/efavirenz (Atripla™). When STRIBILD and Atripla™ are not available, co-formulated Truvada™ (emtricitabine 200 mg / tenofovir disoproxil fumarate 300 mg) plus efavirenz 300 mg may be used. Elvitegravir is an HIV integrase strand transfer inhibitor (HIV-1 INSTI), cobicistat, a CYP3A inhibitor, and emtricitabine and tenofovir DF are both HIV nucleoside analog reverse transcriptase inhibitors (NRTI) and efavirenz is a non-reverse transcriptase inhibitor. All these medications have been licensed for the treatment of HIV-1 infection in humans by the U.S. Food and Drug Administration (FDA).

**Duration:** In Step 1, volunteers will have a cross-sectional evaluation. In Step 2, study participants will have variable times of participation in re-testing until July 2015. In Step 3, individuals with acute and recent HIV-1 infection detected at Step 1 or 2 will be followed for 48 weeks.

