### **Inclusion/Exclusion Criteria:**

In Step 1, potential participants must be MSM and transgender women, have sex with men, HIV status, at high-risk for HIV acquisition. Each potential participant must have the ability and willingness to provide informed consent for study participation, including being tested for HIV-1. If HIV infection is not diagnosed, he must be willing to be enrolled in Step 2, and if diagnosed with acute or recent HIV infection be willing to consider participation in Step 3. In particular, if they are HIV seronegative on antibodies analysis, but with evidence of acute infection (HIV-1

RNA-positive confirmed by HIV antigen analysis), they should be willing to be re-contacted for further HIV testing and linkage to care.

In Step 2, volunteers who were found to have no HIV infection from Step 1 will be re-tested at variable times for incident HIV-1. Roughly, we anticipate testing 800 MSM and transgender women per month and follow-up until July 2015.

In Step 3, men with acute or recent HIV-1 infection detected at Step 1 or Step 2; or individuals who have been diagnosed with HIV in any health clinic or laboratory authorized by the Ministry of Health, and that have had a documented negative result in the past three months with no prior ART exposure, with normal hematological, renal and liver function, will be enrolled in a randomized clinical trial for immediate vs. deferred ART, unless ART initiation criteria are met earlier.

**Treatment Regimen:** In Step 1 and Step 2, no study treatment is offered. All participants will receive standard risk reduction counseling, condoms, and management of STIs. In Step 3, subjects will receive treatment as described above.

Two ART regimens are available:

- STRIBILD, co-formulated elvitegravir/cobicistat/emtricitabine/tenofovir disoproxil fumarate
- ATRIPLA,emtricitabine/tenofovir,DF/efavirenz

Co-formulated elvitegravir/cobicistat/emtricitabine/tenofovir disoproxil fumarate will be the preferred regimen for newly enrolled participants because of the early benefit of integrase inhibitors on the decline of plasma viraemia and co-formulated emtricitabine/tenofovir DF/efavirenz will be an alternative regimen. Participants who have already initiated therapy with emtricitabine/tenofovir DF/efavirenz will continue on this regimen unless they develop clinical indications warranting change in medication.

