### **6.3 STEP 3**

#### **6.3.1 Regimens, Administration, and Duration**

##### **6.3.1.1 Regimen**

Those participants, who have initiated their participation in the study before the approval of **Amendment Letter #1** in this study protocol, will continue their participation as originally programmed.

Once the **Amendment Letter #1** is approved for this study protocol, the participants who are eligible for Step 3 will be given treatment the following way:

- Those people diagnosed with **acute HIV infection** will be offered immediate ART (just at time of the enrollment visit or during the next 48 to 72 hours) for the duration of 48 weeks.

Weeks 0-48: Co-formulated elvitegravir/cobicistat/emtricitabine/tenofovir disoproxil fumarate (or co-formulated emtricitabine/tenofovir DF/efavirenz) orally once daily.

Those people diagnosed with recent HIV infection will be randomized to one of the following arms:

1. Arm 1:

Weeks 0-48: Co-formulated elvitegravir/cobicistat/emtricitabine/tenofovir disoproxil fumarate (or co-formulated emtricitabine/tenofovir DF/efavirenz) orally once daily.

2. Arm 2:

Week 0-24: No treatment unless Peruvian criteria for initiation of treatment are met.

Week 25-48: Co-formulated elvitegravir/cobicistat/emtricitabine/tenofovir disoproxil fumarate (or co-formulated emtricitabine/tenofovir DF/efavirenz) orally once daily.

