##### **6.3.1.2 Administration**

Co-formulated elvitegravir/cobicistat/emtricitabine/tenofovir disoproxil fumarate will be administered as one tablet orally once daily with food. Co-formulated emtricitabine/tenofovir DF/efavirenz will be administered as one tablet orally once daily at bedtime with or without food.

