### **6.3.2 Product Formulation and Preparation**

Elvitegravir/cobicistat/emtricitabine/tenofovir disoproxil fumarate (STRIBILD®) is co-formulated to contain 150 mg of elvitegravir, 150 mg of cobicistat, 200 mg of emtricitabine, and 300 mg of tenofovir disoproxil fumarate, in each tablet. Emtricitabine/tenofovir DF/efavirenz (Atripla™) is co-formulated to contain 200 mg of emtricitabine, 300 mg of tenofovir DF and 600 mg of efavirenz in each tablet. Each bottle contains a silica gel desiccant canister that should remain in the original container to protect the product from humidity. Dispense in the original container. Store at 25°C (77°F), excursions permitted to 15°-30°C (59°-86°F).

Co-formulated emtricitabine/tenofovir (Truvada™) contains 200 mg of emtricitabine and 300 mg of tenofovir DF in each tablet. Each bottle contains a silica gel desiccant canister that should remain in the original container to protect the product from humidity. Dispense in the original container. Store at 25°C (77°F), excursions permitted to 15°-30°C (59°-86°F).

Efavirenz of 600 mg in each tablet, will be dispensed in blister packs of 10 tablets. Store at 25 °C (77°F), excursions permitted to 15°-30°C (59°-86°F).

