### **6.3.3 Product Supply**

Co-formulated elvitegravir/cobicistat/emtricitabine/tenofovir disoproxil fumarate (STRIBILD®) will be provided by Gilead Sciences, Inc while co-formulated emtricitabine/tenofovir DF/efavirenz (Atripla™) will be provided by Merck & Co., Inc., under previous agreement with Gilead Sciences. Co-formulated emtricitabina/tenofovir DF (Truvada™) will be provided by Gilead Sciences. Efavirenz will be purchased locally from commercially available sources.

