## **8.6 SKIN RASH**

In controlled clinical trials, 26% (266/1008) of patients treated with 600 mg efavirenz experienced new-onset skin rash compared with 17% (111/635) of patients treated in control groups. Rash associated with blistering, moist desquamation, or ulceration occurred in 0.9% (9/1008) of patients treated with efavirenz. The incidence of Grade 4 rash (e.g., erythema multiforme, Stevens-Johnson syndrome) in patients treated with efavirenz in all studies and expanded access was 0.1%. Rashes are usually mild-to-moderate maculopapular skin eruptions that occur within the first 2 weeks of initiating therapy with efavirenz (median time to onset of rash in adults was 11 days) and, in most patients continuing therapy with efavirenz, rash resolves within 1 month (median duration, 16 days). The discontinuation rate for rash in clinical trials was 1.7% (17/1008). Co-formulated emtricitabine/tenofovir DF/efavirenz can be reinitiated in patients interrupting therapy because of rash.

Co-formulated emtricitabine/tenofovir DF/efavirenz should be discontinued in patients developing severe rash associated with blistering, desquamation, mucosal involvement, or fever. Appropriate antihistamines and/or corticosteroids may improve the tolerability and hasten the resolution of rash.

Experience with efavirenz in patients who discontinued other antiretroviral agents of the NNRTI class is limited. Nineteen patients who discontinued nevirapine because of rash have been treated with efavirenz. Nine of these patients developed mild-to-moderate rash while receiving therapy with efavirenz, and two of these patients discontinued because of rash.

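### The Summary sets the fallback efavirenz dose at 300 mg, half the only stand-alone tablet the protocol supplies and half the amount in the Atripla it replaces

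*Combined protocol and SAP*

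**What the plan says.** The Intervention paragraph of Section 2 names STRIBILD and Atripla as the study regimens. If neither is available, it permits Truvada (emtricitabine 200 mg with tenofovir DF 300 mg) "plus efavirenz 300 mg may be used". No other place in the protocol text gives a dose for this combination.

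The rest of the protocol treats efavirenz as follows:

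- Section 6.3.2, stand-alone product: "Efavirenz of 600 mg in each tablet, will be dispensed in blister packs of 10 tablets".
- Section 6.3.2, Atripla: 200 mg of emtricitabine, then "300 mg of tenofovir DF and 600 mg of efavirenz in each tablet".
- Section 6.3.1.2, how Atripla is taken: "Co-formulated emtricitabine/tenofovir DF/efavirenz will be administered as one tablet orally once daily at bedtime".
- Section 6.3.3, supply of the stand-alone product: "Efavirenz will be purchased locally from commercially available sources". No strength is given there.
- Section 8.6, background rash data: the figures are for "patients treated with 600 mg efavirenz experienced new-onset skin rash".

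Section 6.3.1.1 offers STRIBILD with one alternative in parentheses, "or co-formulated emtricitabine/tenofovir DF/efavirenz) orally once daily", and does not mention Truvada plus efavirenz. The Treatment Regimen paragraph of the Summary says "Two ART regimens are available" and lists STRIBILD and Atripla only.

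**The concern.** The fallback stands in for Atripla when Atripla cannot be had, so one would expect it to deliver the same three drugs in the same amounts. Two of the three match. The efavirenz amount does not, and it cannot be given as a whole tablet of the only product described.

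A clinician who needs the fallback dose will find it only in the Summary. Following it would give a participant half the efavirenz contained in Atripla. The protocol offers no efficacy or safety information for 300 mg. Viral load is the first primary endpoint (Section 11.2.1), so under-dosing would bear on the participant's care and on that participant's outcome data.

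**Working it through.** No sample size, power or alpha figure is involved. The check is to list every efavirenz amount in the text and compare them.

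**Efavirenz amounts stated**

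| Place | Amount | What it describes |
|---|---|---|
| Section 2, Intervention | 300 mg | dose in the Truvada plus efavirenz fallback |
| Section 6.3.2 | 600 mg | content of one Atripla tablet |
| Section 6.3.2 | 600 mg | strength of the stand-alone tablet |
| Section 8.6 | 600 mg | dose in the trials behind the rash data |

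Three of the four are 600 mg, but they do not carry equal weight. The stand-alone tablet is the direct comparison. Atripla is a different product, relevant because the fallback replaces it. The Section 8.6 figure is background and sets no dose in this study.

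**Component-by-component comparison with the regimen replaced** (daily amounts, one Atripla tablet per day under Section 6.3.1.2)

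| Drug | Atripla | Fallback as written | Ratio |
|---|---|---|---|
| Emtricitabine | 200 mg | 200 mg | 200/200 = 1 |
| Tenofovir DF | 300 mg | 300 mg | 300/300 = 1 |
| Efavirenz | 600 mg | 300 mg | 300/600 = 0.5 |

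The Truvada content in the Summary agrees with Section 6.3.2, so efavirenz is the only component out of line. With 600 mg the ratio becomes 600/600 = 1 and the dose is one whole stand-alone tablet. With 300 mg it is 300/600 = 0.5 of a tablet.

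**Is 300 mg explained anywhere?** The text describes no 300 mg tablet, no splitting and no efavirenz dose reduction. Section 6.3.7.3 allows regimen substitutions for intolerance or toxicity, but it does not deal with supply shortage and gives no efavirenz dose.

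**Where the number may have come from.** In the Summary sentence the efavirenz figure directly follows the tenofovir DF amount, also 300 mg. A number carried over from one drug to the next is plausible. That is inference, and the finding does not depend on it.

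**The case against.** The strongest reply is that this is probably a typing error in a summary paragraph and unlikely to reach a participant. Section 6.3.2 gives a tablet strength, not a dose, so there are not two competing instructions. The 600 mg tablet is described in the treatment section, where a pharmacist would look. Dispensing runs through a prescription and a trained pharmacist (Sections 6.3.4 and 6.3.6), and Section 6.3.7 requires the current package insert to be reviewed when a study agent is started. The Study Specific Procedures, which are not among the documents available, may give the correct dose. Two standard regimens plus a stock-out contingency are not in themselves inconsistent.

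Much of this stands. The finding is a mismatch between a stated dose and a supplied product, and the safeguards lower the risk. They do not remove it. The package-insert rule is aimed at interactions, contraindications and precautions rather than at confirming doses. A pharmacist who caught the problem would have to override the only dose the protocol states. The Treatment Regimen paragraph also refers the reader back to the treatment description above it, which leads to the 300 mg figure. The list of two regimens adds little to the case, and the absence of the fallback from Sections 6.3.1.1 and 6.3.1.2 is a separate omission. It matters here because it leaves the Summary uncorrected.

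**Conclusion.** The concern holds. The Summary's 300 mg is wrong as written: it is half of the only stand-alone efavirenz tablet the protocol describes and half the daily efavirenz in the regimen it replaces. The comparison with Section 6.3.2 is enough to establish this.

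That 600 mg was intended is a strong inference, resting on the match to Atripla and to the supplied tablet. No sentence states it, so the sponsor's clinical team should confirm it. The conclusion is also limited to the text available for review.

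The number of participants affected is not stated and may be none. No sample size, power or analysis figure changes. It should still be fixed, because it is the sole stated dose for an antiretroviral regimen that the study has made supply arrangements for.

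**What to change.** 1. In the Intervention paragraph of Section 2, change the fallback to efavirenz 600 mg, one tablet once daily, once the sponsor's clinical team has confirmed the dose.
2. Add the Truvada plus efavirenz 600 mg fallback, with the condition for its use, to Section 6.3.1.1, and its administration to Section 6.3.1.2.
3. Mention the fallback beside the two regimens listed in the Treatment Regimen paragraph of the Summary, so that the list and the Intervention paragraph agree.
4. Notify the pharmacies at IMPACTA Barranco and IMPACTA San Miguel.

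The cost is one corrected line and a brief mention in the Summary, one added line in each of two sections, and a notice to two pharmacies. Sample size, timeline and analysis are unaffected.

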### **Inclusion/Exclusion Criteria:**

In Step 1, potential participants must be MSM and transgender women, have sex with men, HIV status, at high-risk for HIV acquisition. Each potential participant must have the ability and willingness to provide informed consent for study participation, including being tested for HIV-1. If HIV infection is not diagnosed, he must be willing to be enrolled in Step 2, and if diagnosed with acute or recent HIV infection be willing to consider participation in Step 3. In particular, if they are HIV seronegative on antibodies analysis, but with evidence of acute infection (HIV-1

RNA-positive confirmed by HIV antigen analysis), they should be willing to be re-contacted for further HIV testing and linkage to care.

In Step 2, volunteers who were found to have no HIV infection from Step 1 will be re-tested at variable times for incident HIV-1. Roughly, we anticipate testing 800 MSM and transgender women per month and follow-up until July 2015.

In Step 3, men with acute or recent HIV-1 infection detected at Step 1 or Step 2; or individuals who have been diagnosed with HIV in any health clinic or laboratory authorized by the Ministry of Health, and that have had a documented negative result in the past three months with no prior ART exposure, with normal hematological, renal and liver function, will be enrolled in a randomized clinical trial for immediate vs. deferred ART, unless ART initiation criteria are met earlier.

**Treatment Regimen:** In Step 1 and Step 2, no study treatment is offered. All participants will receive standard risk reduction counseling, condoms, and management of STIs. In Step 3, subjects will receive treatment as described above.

Two ART regimens are available:

- STRIBILD, co-formulated elvitegravir/cobicistat/emtricitabine/tenofovir disoproxil fumarate
- ATRIPLA,emtricitabine/tenofovir,DF/efavirenz

Co-formulated elvitegravir/cobicistat/emtricitabine/tenofovir disoproxil fumarate will be the preferred regimen for newly enrolled participants because of the early benefit of integrase inhibitors on the decline of plasma viraemia and co-formulated emtricitabine/tenofovir DF/efavirenz will be an alternative regimen. Participants who have already initiated therapy with emtricitabine/tenofovir DF/efavirenz will continue on this regimen unless they develop clinical indications warranting change in medication.

**Evaluations:** In Step 1, volunteers will have a cross-sectional evaluation. In Step 2, all participants will be tested quarterly. In Step 3, all participants will be evaluated at regular intervals for primary and secondary outcomes.

